3.4 Treatment Allocation and Methods to Reduce Bias

The order of the pen needle type (current vs. Nucleus) will be randomized for each subject. There will be no masking or blinding in this study.

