6.2 Visit 1: Screening and Enrollment

Prior to screening subjects for eligibility for the study, the PI or designee must obtain written informed consent from all potential subjects. Once consented, subjects will be assigned a subject number.

The following will be conducted by Site Staff to determine eligibility and to collect background/demographical information:

- 6.2.1 **Demographics/Diabetes History:** Subjects will be asked a number of background and demographic questions to ensure they meet the study-specific eligibility criteria. The PI or Investigator will review the medical history information self-reported by the subject; this information will be recorded in the source documents. Information collected will include, but is not limited to age, gender and diabetes history (Type 1 or Type 2, medications including dose and methods of delivery).
- 6.2.2 **Proficiency:** Subjects will be asked to perform a mock injection into an injection pad using a BD Nano pen needle. This will demonstrate their proficiency in injecting with a pen needle and pen device. If the subject is unable to demonstrated proficiency, s/he is discontinued from the study. The study staff will use a checklist to qualify the subject.
- 6.2.3 **Randomization:** After each subject has completed the proficiency test, the subject will be assigned a randomization number based on their pen needle group (Group 1-4), which will determine the order of the pen needed used in Period 1 or Period 2.

6.2.4 Visit 1

Non Wash-in Users

- Subjects will be randomized to Nucleus pen needle for the first 15-day period, then assigned commercial 32G pen needle for the second 15-day period OR assigned to commercial 32G pen needle for the first 15-day period, then the Nucleus pen needle for the second 15-day period (See randomization schedule).
- Subject will be instructed to use only the assigned pen needle during Period 1. If the subject is assigned to the Nucleus pen needle, they will be provided enough of the assigned pen needles until their scheduled return visit of 15-days. If the subject is assigned to the commercial 32G pen needle, they will use their current pen needle until the scheduled return visit of 15 days.
- Subject will be given a Diary 1 log to report events and answer questions during Period 1. Subjects will be trained on diary documentation.

Wash-in Users

- Subjects will be assigned a wash-in randomization number to determine their pen needle group (Group 1-4).

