3.3 Study Design

This is a multi-site, prospective, open-label, randomized, 2-period crossover (15 days per period) study comparing commercially available 32G pen needles to the BD Nucleus pen needle. BD Nucleus will be compared to four groups of pen needles:

- Group 1: BD Nano (32Gx4mm)
- Group 2: NovoFine (32Gx6mm)
- Group 3: NovoFine Plus (32Gx4mm) & NovoTwist (32Gx5mm)
- Group 4: Other 32G (such as UltiMed, MHC, or other private label)

Approximately 25% of the subjects are expected to be Type 1 patients and the remaining 75% are expected to be Type 2 patients.

The study is targeting 260 subjects. A total of 240 subjects are needed with an additional 20 subjects for subjects lost to follow up or other significant protocol deviations. Each group will consist of approximately 60 subjects. Each subject will be screened to determine eligibility into the study. Subjects entering the study who are currently injecting with one of the above mentioned pen needles will automatically be enrolled in their respective group. For example, if a subject comes in using the BD Nano, they will be enrolled in Group 1. If their current pen needle group has completed enrollment, they will be eligible for wash-in (see below).

To facilitate recruitment, a 14 day wash-in period will be allowed in the following situations:

- As BD holds the vast majority of the Pen needle market share in the US, enrolling subjects using non BD brands will be difficult. Subjects currently using a 32G pen needle of 4, 5 or 6 mm lengths will be allowed to wash-in if their current pen needle group has completed enrollment of 60 evaluable subjects. These subjects will be eligible to wash-in to the next available applicable group, per the Wash-In randomization schedule. The length of their current pen needle will be maintained.

- For subjects currently using a 31G pen needle of 4, 5 or 6 mm lengths provided the subject is willing to switch to an assigned commercially available 32G pen needle for the duration of the study. These subjects will be eligible to wash-in to an available applicable group, per the Wash-In randomization schedule. The length of their current pen needle will be maintained.

Wash-in subjects will be randomized as follows (cf. Wash-in randomization schedule):

- If subject is currently on a 31G x 4mm or 32G x 4mm they will get randomized to either Group 3 (Novo Fine Plus (32Gx4mm)) or Group 4 (UltiCare Micro 32Gx4mm).

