7.2.2.1 Analysis of Relative VAS Score

For each outcome measured on a relative VAS, a two-sided 95% confidence intervals will be calculated for the average rating. A modeling approach will be used to adjust for the order effect (because of the often observed bias towards favoring the last PN used). A linear model will be used to evaluate the pen needle group effect on the response to test whether the groups can be combined (a p-value < 0.05 for the pen needle group effect indicates non-poolability). In the model, the order of the pen needles used and the group to which the subject belongs based on their currently used or assigned pen needle will be used as covariates. LS means with CI will be obtained from the model and tested for non-inferiority, followed by superiority.

- If the lower bound of the CI is $> -10\text{mm}$, we can conclude in non-inferiority.
- If the lower bound of the CI is $> 0\text{mm}$, we can conclude in superiority.

Additional analysis: a *wash-in* indicator and an *Asian* indicator may be used to investigate these effects, as well as a site effect.

```
> #####
> ## Example R code to fit a linear model
> #####
> ##
> ## fitting the model
> model.fit=lm(vas_analysis ~ (NUCL_ORDER + PN_GROUP + ASIA)^2 + WASH_IN,
+             data=dataset, na.action=na.omit)
> #ANOVA table
> ## if p-value for PN_GROUP < 0.05, results not poolable across Groups
> anova(model.fit)
```

Analysis of Variance Table

Response: vas_analysis

	Df	Sum Sq	Mean Sq	F value	Pr(>F)
NUCL_ORDER	1	192	191.7	0.0928	0.7612
PN_GROUP	3	2757	919.0	0.4446	0.7215
ASIA	1	3215	3215.0	1.5554	0.2144
WASH_IN	1	751	750.8	0.3632	0.5477
NUCL_ORDER:PN_GROUP	3	3991	1330.3	0.6436	0.5882
NUCL_ORDER:ASIA	1	131	130.8	0.0633	0.8017
PN_GROUP:ASIA	3	308	102.6	0.0496	0.9853
Residuals	139	287317	2067.0		

```
> ##example contrast for the different pen needle groups
> ## given results not poolable,
> ## to identify which groups are not poolable
> ##
> model.fit=lm(vas_analysis ~ NUCL_ORDER + PN_GROUP,
+             data=dataset,
+             na.action=na.omit)
> ##
> library(multcomp)
> confint(glht(model.fit, linfct = mcp(PN_GROUP = "Tukey")))
```

Simultaneous Confidence Intervals

Multiple Comparisons of Means: Tukey Contrasts

```
Fit: lm(formula = vas_analysis ~ NUCL_ORDER + PN_GROUP, data = dataset,
na.action = na.omit)
```

Quantile = 2.5914

95% family-wise confidence level

Linear Hypotheses:

	Estimate	lwr	upr
Group 2 - Group 1 == 0	-9.0440	-33.6940	15.6060

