7.2.2.2 Needle Bending, Injection site Bleeding and Bruising

For each pen needle group, a 95% confidence interval for the following difference in two independent proportions will be calculated using the score method.

$$\text{Proportion with BD Nucleus PN} - \text{Proportion with Current/Assigned PN}$$

Results will be tested for non-inferiority: If the upper bound of the CI is $< 4\%$, we can conclude in non-inferiority.

If results are poolable, results will also be presented for the groups combined. Poolability will be assessed through a mixed effects logistic regression model including a PN group by PN type interaction. If the interaction is significant, results are not poolable and only poolable groups will be presented combined.

```

> #####
> ## Example R code to test the difference in proportion of response
> #####
>
> ## Two-Sample difference in proportion test
>
> propdat <- data.frame(Break=c(45,56),NoBreak=c(780,810))
> row.names(propdat) <- c("BD Nucleus","Comparator")
> propdat$Total <- rowSums(propdat)
> propdat$Proportion <- propdat$Break/propdat$Total
> #
> library(PropCIs)
> ## 95% confidence interval
> #
> proptestci <- diffscoreci(x1=propdat["BD Nucleus","Break"],
+                           n1=propdat["BD Nucleus","Total"],
+                           x2=propdat["Comparator","Break"],
+                           n2=propdat["Comparator","Total"],
+                           conf.level=0.95)$conf.int
> #
> propest <- propdat["BD Nucleus","Proportion"] -
+   propdat["Comparator","Proportion"]
> #
> #if upper bound of CI < 0.04, NI satisfied
> data.frame(Estimate=propest,
+            CI = paste0("(",proptestci[1],", ", ",proptestci[2],")"))

```

Estimate	CI
1 -0.01011967	(-0.0330320064995986, 0.0127257649847972)

```

> #####
> ## Example R code for poolability testing
> #####
> library(lme4)
> ## mixed effects logistic regression model
> model = glmer(BLEEDING ~DEMO_PN_GROUP*RS_PN + (1 |SUBJ_ID),
+             data=diary, family=binomial,
+             control = glmerControl(optimizer = "bobyqa"))
> library(car)
> #if interaction p-value < 0.05, group results not poolable
> #

```

```

> Anova(model,type="III")

```

Analysis of Deviance Table (Type III Wald chisquare tests)

Response: BLEEDING

	Chisq	Df	Pr(>Chisq)
(Intercept)	186.7400	1	< 0.000000000000000022
DEMO_PN_GROUP	3.3702	3	0.337994
RS_PN	8.8563	1	0.002921
DEMO_PN_GROUP:RS_PN	14.6710	3	0.002120

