7.2.2.3 Analysis of Leakage

Distribution of leakage scores will be provided and proportion of injections with recorded leakage score >0 will be calculated per Pen Needles in each subgroup. Analysis as in Section 7.2.2.2 will be performed using the proportion of injections with recorded leakage score > 0 as response.

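### The diary poolability model leaves out period, so a Diary 1 to Diary 2 change in event rates can make alike groups look non-poolable; adding the term is a free, low-severity improvement

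*SAP*

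**What the plan says.** SAP 3.3 describes a "2-period crossover (15 days per period) study". Protocol 3.4 adds: "The order of the pen needle type (current vs. Nucleus) will be randomized for each subject". Under Protocol 6.2, "the subject will be assigned a randomization number based on their pen needle group (Group 1-4"), so order is randomised within group. No ratio or block size is given.

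For the yes/no diary items, SAP 7.2.2.2 says: "Poolability will be assessed through a mixed effects logistic regression model including a PN group by PN type interaction". The example code fits "model = glmer(BLEEDING ~DEMO_PN_GROUP*RS_PN + (1 |SUBJ_ID"), that is, group, needle, their interaction and a random subject intercept. The decision rule is in a code comment: "if interaction p-value < 0.05, group results not poolable". If it is triggered, only the poolable groups are shown combined. SAP 7.2.2.3 carries this over to leakage: "Analysis as in Section 7.2.2.2 will be performed using the proportion of injections with recorded leakage score > 0 as response".

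For the VAS outcomes SAP 7.2.2.1 does otherwise: "A modeling approach will be used to adjust for the order effect (because of the often observed bias towards favoring the last PN used"), with order as a covariate in the model that tests poolability. Protocol 13.3 mentions a visit adjustment only for the VAS. No section adds a period or order term for the diary outcomes.

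**The concern.** In a two-period crossover, any change in recorded events from Diary 1 to Diary 2 that is common to both needles (reporting fatigue, or getting used to the diary) stays in the needle contrast unless period is modelled. It cancels within a group only if the two orders carry equal event weight there. Randomisation balances head counts in expectation, but not events, which may come from a minority of subjects with very different injection frequencies. The leftover imbalance differs between groups by chance and looks like a group-by-needle interaction.

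The interaction p-value decides which groups enter the all-groups-combined result for bending, bleeding, bruising and leakage, a secondary objective in SAP 3.2.2. A false rejection narrows that result for a reason unrelated to the comparators.

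**Working it through.** **The plan's own figure.** The example output in SAP 7.2.2.2 shows an interaction chi-square of 14.6710 on 3 df with p = 0.002120. P(chi-square with 3 df > 14.671) = 0.00212, so it reproduces, and the poolability test is a 3-df Wald test. No operating characteristics are stated for it.

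**Mechanism.** Let δ be the log odds ratio for Period 2 against Period 1, and w the share of a group's event weight from subjects who have Nucleus in Period 2. With no needle effect, the apparent needle log odds ratio is about (2w − 1)δ.
- w = 0.5: 0, so the shift cancels.
- w = 0.6, odds ratio 1.5: 0.2 × 0.405 = +0.08.
- w = 0.4, odds ratio 1.5: −0.2 × 0.405 = −0.08.

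Two alike groups with these weights differ by 0.16 on the log-odds scale. Averaged over randomisations w is 0.5, so there is no systematic bias. The fault is extra variance, which the model's standard error does not contain.

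**Inputs.**
- Four groups of about 60 (SAP 3.3), two-sided 5% (SAP 7.2).
- Event rate 4%. Illustrative Table 5 gives (175 + 198)/(4658 + 4619) = 373/9277 = 4.0%.
- Clustering: in illustrative Table 6, 34.5% to 45.8% of subjects have any bleeding. A random-intercept SD of 2.0 to 2.06 gives about 40-42%.
- Injections per day: the overall mix in illustrative Table 11 (42, 43, 61, 50 and 34 of 230 for one to five), times 15 days.
- Period effect: not in the documents. Assumed odds ratios are 1.00, 0.80, 0.67 and 0.50, or the mirror values 1.25, 1.5 and 2.0.

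SAP 11 says the example tables hold unrepresentative test data. They only set the range.

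**Simulated false non-poolability** (no group or needle difference, 1:1 order within group; replicates in brackets). The 600-replicate runs use SD 2.0 and the mirror odds ratios; the others use SD 2.06.

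| Period odds ratio | As written | With period term |
|---|---|---|
| 1.00 | 4.9% (1500), 5.5% (600), 5.0% (300) | 5.8% (600), 5.0% (300) |
| 0.80 | about 8% (1500), 6.8% (600), 6.8% (400), 6.7% (300) | 5-6%, 5.5%, 5.0%, 4.7% |
| 0.67 | 13.7% (1500), 13.0% (600), 11.5% (400), 9.3% (300) | 5-6%, 6.5%, 5.3%, 2.3% |
| 0.50 | 30.2% (500), 26.5% (600), 25.7% (300) | 4.0%, 4.2%, 7.0% |

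The Monte Carlo standard error of the 9.3% is √(0.093 × 0.907/300) = 1.7 points. The larger runs at 0.67 sit near 13-14%.

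**Sensitivity, as written.**
- Less clustering at 0.67: 10.6% (SD 1.5) and 8.8% (SD 1.0).
- 45 per group: 11.2% at 0.67 and 26.7% at 0.50.
- Simple randomisation of order: 14.8% at 1.5 and 32.7% at 2.0. Splits of 36/24 alternating with 24/36: 22.0% and 43.2%. With the term, these four are 3.8% to 5.8%.
- Rare events (assumed 0.5%) at 0.67: 3.8% and 4.7% in two runs, against 4.0% in both with the term. No inflation.
- Common events, such as leakage above 0 (64% to 93% in illustrative Table 8): about 12% at 0.67.

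**If effects vary between subjects** (assumed log-odds SD 0.5, two runs where two figures are given).
- Varying period change, mean odds ratio 0.67: 29.7% falls to 22.3%, and 32.5% to 25.8%, when the term is added.
- Varying period change, no mean shift: about 22% in one run; 25.0% without and 26.0% with the term in the other.
- Varying needle effect, no period effect: 21.5% without and 20.8% with.

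**The 4% interval.** With a true difference of 4 points, the rate of concluding non-inferiority moves only from 12.2% to 13.1% when a period change is present. That level is high for other reasons and is not part of this point.

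**The case against.** The strongest reply is that the size rests on a period effect the documents never give. That stands. A reader might take the VAS remark about favouring the last needle as evidence for one. It is not: it concerns a single comparative rating at the end of the study, whereas diary items are recorded after each injection. At 0.80 the inflation is small.

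A second reply is that a period term is not excluded: the code is labelled an example, and the text says only that the model includes the interaction. True, but none is planned, and adding one after seeing the data would be a post hoc choice about a gatekeeping test.

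Third, the consequence is limited. Group results are always presented first (SAP 7.2.2), and a significant interaction narrows the combined result without removing any group's own result. This also stands.

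Three stronger readings are tempting and not supported:
- That the needle comparisons or the non-inferiority conclusions are biased by period. Order is randomised within group, and the 4% interval barely moves.
- That all four diary outcomes are affected alike. Events as rare as 0.5% show no inflation.
- That one added term restores a 5% error rate. It does so only if the period shift and the needle effect are the same for every subject.

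**Conclusion.** The omission is certain in both text and code, and the mechanism is sound. When diary event rates change between periods, the rule rejects poolability for alike groups more often than 5%, unless events are rare. Assuming a 4% event rate, clustering as in the illustrative tables, 60 per group and balanced order, the rate is about 7-8%, 9-14% and 26-30% at odds ratios of 0.80, 0.67 and 0.50. Less clustering lowers it; unbalanced order raises it. If no period change occurs, nothing is lost as written.

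What is at stake is which groups enter the combined secondary diary results. The primary VAS analysis already adjusts for order. Severity is low, and the change is worth making because it is free.

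**What to change.** In SAP 7.2.2.2, and so by reference in 7.2.2.3, add period (Diary 1 or Diary 2) as a fixed effect, for example `glmer(BLEEDING ~ PERIOD + DEMO_PN_GROUP*RS_PN + (1|SUBJ_ID), ...)`, and take the poolability p-value for the group-by-needle interaction from that model. This brings the diary model into line with the VAS model.

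The cost is one line of text, one term in the code and one degree of freedom per model. No new data are needed, because the two diaries are separate logs. The SAP should not claim that this secures a 5% error rate: between-subject variation in the period or needle effect is not covered by a random intercept alone.

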7.2 Analysis Method

This section provides a detailed description of the statistical analysis that will be performed in this study.

Unless otherwise stated, all the statistical tests are two-sided at a significance level of 5% and adjustment will be made for multiple comparisons when appropriate.

All the primary and secondary endpoints will also be analyzed as described below for the Asian sub-population.

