7.2.2.4 Analysis of Exploratory Objectives (Non-Comparative Questionnaire and Needle Breaking)

All the Exploratory binary responses (Yes / No) will be summarized with proportion of “Yes” answers and 95% confidence interval (score method) per pen needle group and overall.

In addition, for each pen needle group, a 95% confidence interval for the Proportion “Yes” with the BD Nucleus PN vs the Proportion “Yes” with the Current/Assigned PN will be calculated using the score method for independent proportions.

8 Safety Analysis

Data listings will be provided for any adverse events and serious adverse events in Appendix. The events will also be summarized descriptively per pen needle and study group. No safety analysis is planned.

9 Interim Analysis

Interim analyses will be performed for information only with no alpha adjustment.

10 Additional Analysis

A sub-group with Asian ethnicity, all study groups combined, will also be evaluated for the objectives listed in Section 3.2.1 and 3.2.2.

The primary endpoint may also be evaluated within each subgroups based on whether the patients had washout period before randomization.

11 Example Reports

This section provide examples of tables and graphical representations that will be provided in the study statistical report. These table examples were generated using the sample data available from the data base test framework which do not provide an exhaustive or representative example of the values and levels that will be obtained in the study. They are intended to provide illustrative examples of the tables and figures that will be included in the final statistical analysis report.

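### The diary poolability test shown in the SAP is a Wald chi-square, which loses sight of any group with an event-free cell, so an outlying group can be pooled when the other groups are alike

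*SAP*

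**What the plan says.** SAP 7.2.2.2 states: "Poolability will be assessed through a mixed effects logistic regression model including a PN group by PN type interaction". It continues: "If the interaction is significant, results are not poolable and only poolable groups will be presented combined". The prose names no test statistic. The example code fits an unpenalised model, "model = glmer(BLEEDING ~DEMO_PN_GROUP*RS_PN + (1 |SUBJ_ID", with a random intercept per subject. It then makes a Type III call to `Anova`, whose output is headed "Analysis of Deviance Table (Type III Wald chisquare tests". The code comment gives the decision rule: "if interaction p-value < 0.05, group results not poolable". SAP 7.2 sets the general level: "all the statistical tests are two-sided at a significance level of 5" percent.

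SAP 7.2.2.3 sends leakage through the same method, and SAP 7.2 extends the secondary analyses to the Asian sub-population. SAP 7.2.2 and Protocol 13.3 repeat the pooling principle without naming a test. None of these sections says what to do when a cell has no events.

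**The concern.** A poolability test should catch one group that behaves differently from the rest. A Wald test on an unpenalised logistic fit can miss such a group when the difference is most extreme. With no events for one needle in one group, that group's log odds ratio has no finite estimate. The fitted coefficient drifts to a large value, its standard error grows far faster, and the group drops out of the statistic. What remains reflects only the differences among the other groups.

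At stake is the combined result for bending, bleeding, bruising and leakage. SAP 3.2.2 lists this as a secondary objective alongside the per-group results, and SAP 3.1 says the outcomes are meant to support marketing claims. A combined figure could be presented as common to all comparators when one comparator differs.

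**Working it through.** **The plan's own figures.** The example output reads "DEMO_PN_GROUP:RS_PN 14.6710 3 0.002120". The upper tail of a chi-square on 3 df at 14.671 is 0.00212, so the p-value reproduces. The chi-square itself cannot be rebuilt without subject-level diaries. A fixed-effect logistic fit to the Table 5 bleeding counts (28 to 90 events per cell) gives Wald 7.90 and likelihood ratio (LRT) 7.95. With no sparse cells the two tests agree.

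**A zero cell.** Denominators are from SAP Table 5: Nucleus 2142, 857, 1023, 636; comparator 1998, 1020, 906, 695. The event counts are assumed. Fits are fixed-effect logistic. Groups 1 to 3 are held at 10/10, 4/5 and 5/4 (Nucleus/comparator).

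| Group 4 | Wald (3 df) | p | LRT (3 df) | p |
|---|---|---|---|---|
| 6/0 | 0.047 | 0.997 | 8.17 | 0.043 |
| 8/0 | 0.047 | 0.997 | 10.55 | 0.014 |
| 15/0 | 0.047 | 0.997 | 17.93 | 0.0005 |
| 15/1 | 6.92 | 0.074 | 12.35 | 0.006 |

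At 15/0 the Group 4 interaction coefficient is about 25.6 with a standard error of about 84,763. Its squared ratio, (25.6/84,763)² ≈ 9 × 10⁻⁸, is nil. The remaining 0.047 comes from Groups 1 to 3, which is why it does not move as Group 4 goes from 6/0 to 15/0.

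**With a subject random intercept.** Diaries were simulated with 60 subjects per group, an assumed 36 injections per period and an assumed subject SD of 1.5. One cell was empty against 34 to 68 events, and the other groups were homogeneous. Wald p ran from 0.053 to 0.82; LRT p was below 10⁻¹⁰ throughout.

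**Limits of the effect.**
- If the other groups truly differ, Wald still rejects (46 to 49 in the simulated diaries).
- With the other three groups at 20 per 1000 on both needles, 1 against 20 gives Wald p = 0.039, so it rejects; 0 against 20 gives Wald p = 1.00 and LRT p = 1.5 × 10⁻⁵.
- With the other three groups at 3 per 1000, the LRT needs about 0 against 8 (p = 0.035). At 0 against 6 its p is 0.078, so neither test rejects.

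**How likely is an empty cell at the planned size?** Injections per subject are Table 5 injections divided by Table 6 subjects. For Group 4 this is 636/24 = 26.5 (Nucleus) and 695/21 = 33.1 (comparator). Times 60, the cells are 2178, 1904, 2046, 1590 (Nucleus) and 2220, 2110, 1874, 1986 (comparator). With independent injections at a common rate r, P(any empty cell) = 1 − Π[1 − (1 − r)^n].

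| Assumed rate | 60 in every group | 60 in Group 1, 45 in Groups 2–4 |
|---|---|---|
| 0.5% | 0.06% | 0.6% |
| 0.3% | 2.4% | 8.6% |
| 0.2% | 15% | 32% |

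Subject clustering would raise these.

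**Power.** Assume Group 4 at 2% (Nucleus) against 0.1% (comparator) and the other groups at 0.5% on both needles. At 60 per group, simulation with independent injections gives Wald about 86–88% and LRT nearly 100%. The shortfall matches the chance that the 0.1% cell is empty: 0.999^1986 ≈ 14%. With 45 in Groups 2–4 the figures are about 73% and 99%.

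**Asian sub-population.** Protocol 4.1 seeks at least 30 subjects. Split evenly (an assumption) that is 7.5 per group. At 26.5 to 37 injections per subject there are about 200 to 280 injections per cell, or 1.0 to 1.4 expected events at a 0.5% rate. Empty cells would be common, though no test has much power there.

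**The case against.** Several points on the other side stand.

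- The Wald test appears only in code labelled as an example and run on bleeding; the prose requires the model, not the statistic. But the code is then the only specification, and if it does not bind, the test is unspecified. The remedy is the same.
- Example bleeding and leakage events are frequent, so at such rates neither endpoint is exposed. At 2.7%, even the Table 5 denominators give an empty-cell chance of about 3 × 10⁻⁸.
- Group differences would not be hidden, because SAP 7.2.2 presents each group first, with its own interval.

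A reader might infer more than the documents support.

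- *That the Wald statistic generally collapses to zero.* It does so only when the remaining groups are alike.
- *That power is almost lost.* On the Table 5 denominators the scenario above gives about 21% (Wald) against 87% (LRT), and empty-cell chances of 10%, 42% and 73%. Those denominators are sample data (SAP section 11: "These table examples were generated using the sample data available from the data base test framework") from only 21 to 59 subjects per cell in Table 6, below the planned size.
- *That an empty-cell chance is an error chance.* It was computed under one common rate, where pooling is correct.
- *That non-inferiority conclusions are wrong.* In the 15/0 example Group 4 differs by +2.4% (1.4% to 3.9%), the pooled result by +0.3% (0.01% to 0.65%), and Groups 1 to 3 together by about 0% (−0.3% to 0.3%). Every upper bound is below the 4% margin.

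**Conclusion.** The concern holds in a limited form. Run as shown, the test can declare a sharply different group poolable when that group has an event-free cell, the opposite cell holds a sizeable count (roughly 6 to 8 events or more in the constructed cases) and the other groups are alike. It is also conservative when a cell has very few events. Exposure is limited to rare events: chiefly needle bending, and possibly the Asian sub-population. The consequence is confined to which groups enter the combined secondary diary result. The per-group intervals and their non-inferiority conclusions are unaffected, as is the primary VAS analysis, which uses a linear model.

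The size rests on assumed event rates, on injections per subject taken from sample data, and on independent injections. At planned numbers, in the scenario tested, the loss is about 12 to 14 percentage points of power (86–88% against nearly 100%), rising to about 26 points (73% against 99%) with 45 in Groups 2–4. This is a worthwhile correction to a secondary analysis, not a threat to the main conclusions.

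**What to change.** In SAP 7.2.2.2, replace the Type III `Anova` call with a likelihood-ratio comparison of the models with and without `DEMO_PN_GROUP:RS_PN`, that is `anova(m0, m1)`. State in the text that this is the poolability test for bending, bleeding, bruising and leakage.

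The cost is one extra model fit, a line or two of code and a sentence of text. The downside is that at sparse counts the LRT rejects somewhat too often, about 7–8% in simulation against 0–2% for Wald. That errs towards not pooling. A parametric-bootstrap p-value for sparse cells would correct it, but it needs more programming and is optional. Like the Wald test, the 3-df LRT shows that groups differ, not which one. The SAP gives no step for identifying that group for diary endpoints, and pairwise Wald contrasts would fail in the same way at an empty cell.
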